14.3 SECONDARY EFFICACY ANALYSES

The secondary efficacy endpoints in this study are defined in section 3.2.2.

Unless otherwise specified, analyses of secondary efficacy endpoints are based on the FAS.

For dichotomous secondary efficacy endpoints, subjects who early withdraw from the study for any reason will be considered as non-responders at each post-withdrawal assessment time point. Descriptive summaries of secondary efficacy endpoints will be based on non-missing data only.

For continuous secondary efficacy endpoints, missing values will not be imputed.

For comparison of dichotomous endpoints, if both the expected number of subjects achieving response and the expected number of subjects not achieving response are ≥ 5 in each treatment group, the normal approximation method will be used for analysis; otherwise, Fisher's exact method described in Section 14.4.1 will be used instead.

14.3.1 Percentage of subjects achieving IGA response at Week 1, Week 4, Week 8

Rates of IGA response at other specified efficacy assessment point (Week 1, Week 4, and Week 8) will be analyzed using the method of normal approximation to binomial or Fisher's exact test.

14.3.2 Percentage of EASI change from baseline at Weeks 1, 4, 8, and 12

The EASI score is the sum of the skin lesion severity scores and the integral and coefficient product of the area affected by the skin lesions in the four parts of the body: head and neck, trunk, upper limbs, and lower limbs. The EASI score ranges from 0.0 to 72.0 and can be varied in increments of 0.1. Higher scores indicate greater severity.

A mixed-effects repeated measures model (MMRM) will be used to analyze percentage of EASI change from baseline including treatment group, baseline value, visit, and treatment-by-visit interaction as fixed effect and visit as repeated variable. An unstructured covariance matrix will be used to model the within-subject variance-covariance errors. If model fails to converge, the following options will be considered in order until convergence achieved: TOEPH (Heterogeneous Toeplitz) 、 AR(1)(Heterogeneous autoregressive) 、 TOEP(Toeplitz) and CS (Compound symmetry). The Kenward-Roger approximation will be used to estimate the degrees of freedom. The comparisons of interest will be the contrasts between each active dose and placebo at every time point. For the treatment difference of each active dose versus placebo at each visit, the model estimated least square means, standard error, p-value, and two-sided 90% confidence interval will be reported.

Referenced MMRM SAS code:

```
PROC MIXED DATA=adam.adeff METHOD=REML;  
  CLASS treat visit subj;  
  MODEL chgEASI= treat visit treat*visit basval /SOLUTION DDFM=KR;  
  REPEATED visit/SUBJECT=subj TYPE=UN;  
  LSMEANS treat*visit/DIFF PDIFF CL;  
  RUN;
```

In the above code, variables are defined as follows:

ChgEASI = change from baseline in EASI for each visit

Treat = treatment group

Visit = visit

Subj = subject

Basval = baseline EASI score

Least square means of change from baseline in EASI score at each assessment visit will be graphically displayed for each treatment using a line plot.

EASI score and change from baseline will be summarized by treatment at each efficacy assessment visit, and statistics including mean, standard deviation, and 90% confidence interval will be provided. Same statistics will also be provided for each site score as well as for the four symptoms.

14.3.3 Percentage of subjects with $\geq 50\%$, 75% , and 90% EASI improvement from baseline (EASI50, EASI75, EASI90) at Weeks 1, 4, 8, and 12

Percentage of EASI change from baseline will also be derived as a dichotomous result according to the following three criteria: $\geq 50\%$ (EASI50), $\geq 75\%$ (EASI75), and $\geq 90\%$ (EASI90). For each derived dichotomous EASI result, the comparison between 4 mg QD and 8 mg QD versus placebo will be performed by method of normal approximation to binomial or Fisher's exact test, respectively, according to actual data distribution.

The number and percentage of subjects achieving EAS50, EAS75, and EAS90 will also be summarized for each treatment group at each efficacy assessment visit.

14.3.4 Change from baseline in SCORAD at Week 1, Week 4, Week 8, and Week 12

The SCORAD score integrates the observational assessment of physicians and patients. The scoring scale consists of three major sections: the objective signs section includes lesion area and lesion severity, and the subjective symptoms include the degree of itching and sleep effects. SCORAD scores range from 0 to 103.

SCORAD quantitative results will be analyzed using the same MMRM method as EASI.

The SCORAD scores and change from baseline at each assessment visit will be summarized, and the scores of each objective sign sections (lesion area, lesion severity) and the subjective symptom (pruritus, impact on sleep) will be summarized using statistics including mean, standard deviation and 90% confidence interval. A line graph will be used to graphically display the least squares mean of change from baseline in SCORAD score for each treatment assessment visit (including five scales: Total Score, A Lesion Area, B Lesion Severity, C Pruritus and sleeplessness).

14.3.5 Percentage of subjects With $\geq 50\%$, 75% , and 90% SCORAD improvement from baseline (SCORAD50, SCORAD75, SCORAD90) at Weeks 1, 4, 8, and 12

Percentage of SCORAD change from baseline will also be derived as a dichotomous result based on the following three criteria: $\geq 50\%$ (SCORAD50), $\geq 75\%$ (SCORAD75), and $\geq 90\%$ (SCORAD90). For each derived dichotomous SCORAD result, the comparison between 4 mg QD and 8 mg QD versus placebo will be performed using method of normal approximation to binomial or Fisher's exact test, respectively, according to actual data distribution.

The number and percentage of subjects achieving SCORAD50, SCORAD75 and SCORAD90 will also be reported.

14.3.6 Percent of pruritus numerical Rating scale (NRS) change from baseline at Weeks 1, 4, 8, and 12

At each visit, the degree of pruritus/scratching is assessed by the subject on an 11-grade rating scale from 0 (no pruritus/scratching) - 10 (severe pruritus/scratching) for the first 24 hour of the visit.

The NRS quantitative results will be analyzed using the same MMRM method as for EASI.

The NRS score and change from baseline at each efficacy assessment visit will be summarized by treatment and mean, standard deviation and 90% confidence interval will be provided.

14.3.7 Percentage of subjects achieving pruritus NRS improvement ≥ 3 from baseline in at Weeks 1, 4, 8, and 12

Percentage of NRS change from baseline will also be derived into two categories: ≥ 3 points and < 3 points. Dichotomized NRS results will be compared between 4 mg QD and 8 mg QD versus placebo groups using method of normal approximation to binomial or Fisher's exact test, respectively, according to actual data distribution, noting that the comparison of NRS differences will only be performed in the population with baseline NRS score ≥ 3 .

The number and percentage of NRS will also be reported as follows: 0, 1-3, 4-6, 7-9 and 10 points for 5 grades.

14.3.8 Change from baseline in dermatology life quality index (DLQI) at Weeks 1, 4, 8, and 12

The DLQI is a dermatology-related questionnaire that allows subjects to assess the impact of skin disease on quality of life through 10 questions with total score ranging from 0 to 30.

The rules for scoring the 10 questions are as follows:

- Not at all: 0 points (Item 7 Question: No (Not at all), 0 points);
- A little: 1 point (question 7: no (a little), 1 point);
- Many: 2 points (question 7: No (many), 2 points);
- Very much: 3 points (question 7: Yes, 3 points).

Change from baseline in DLQI will be analyzed using the same MMRM model as the EASI.

The DLQI score and change from baseline at each treatment visit will be summarized using statistics including mean, standard deviation, and 90% confidence interval.

14.3.9 Change from baseline in biomarker IgE at Weeks 1, 4, 8 and 12

Atopic dermatitis is divided into endogenous and exogenous types. Patients with exogenous AD usually present with elevated serum total IgE.

Change from baseline in IgE will be analyzed using the same MMRM model as the EASI.

IgE and change from baseline will be summarized by treatment group at each efficacy assessment visit using statistics including mean, standard deviation and 90% confidence interval.

14.3.10 Change in absolute eosinophil count from baseline at Weeks 1, 4, 8, and 12

The change from baseline in absolute eosinophil count will be analyzed using the same MMRM model as described for the EASI.

Absolute eosinophil counts and changes from baseline will be summarized by treatment group at each efficacy assessment visit using statistics including mean, standard deviation, and 90% confidence intervals.

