9.2.2 Analysis of the secondary efficacy endpoints

All secondary endpoints for each drug group and placebo control will also be analyzed.

For dichotomous secondary endpoints (percentage of subjects achieving IGA response at other follow-up time points except Week 12; percentage of subjects achieving \geq 50%, 75%, and 90% improvement from baseline in EASI scores at Weeks 1, 4, 8, and 12 (EASI50, EASI75, EASI90); percentage of subjects achieving \geq 50%, 75%, and 90% improvement from baseline in SCORAD at Weeks 1, 4, 8, and 12 (SCORAD50, SCORAD75, SCORAD90); percentage of subjects achieving \geq 3 points improvement from baseline in pruritus NRS at Weeks 1, 4, 8, and 12), the method of normal approximation will be used for analysis.

For continuous secondary endpoints (percent change from baseline in EASI scores at Weeks 1, 4, 8, and 12; change from baseline in SCORAD at Weeks 1, 4, 8, and 12; percent change from baseline in pruritus numeric rating scale (NRS) at Weeks 1, 4, 8, and 12; change from baseline in Dermatology Life Quality Index (DLQI) at Weeks 1, 4, 8, and 12; and change from baseline in biomarkers hsCRP and Ig E at Weeks 1, 4, 8, and 12.), a mixed-effects repeated measures model (MMRM) will be used for analysis. Fixed effects in the model were treatment group, baseline value, visit, and treatment-by-visit interaction, with random effects for subject.

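### The MMRM holds the baseline slope constant over Weeks 1 to 12; a baseline-by-visit term costs almost nothing and may sharpen the later-visit contrasts if that slope changes over time.

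*SAP*

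**What the plan says.** SAP 14.3.2 gives the reference code for percentage change in EASI. The class statement is "CLASS treat visit subj" and the model statement is "MODEL chgEASI= treat visit treat*visit basval /SOLUTION DDFM=KR". Baseline is not a class variable and appears once, so it has one regression coefficient for all visits.

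The SAP text agrees with the code, listing a model "including treatment group, baseline value, visit, and treatment-by-visit interaction as fixed effect and visit as repeated variable". Protocol 9.2.2 has the same terms: "Fixed effects in the model were treatment group, baseline value, visit, and treatment-by-visit interaction". The common slope is therefore the intended specification and not a coding slip.

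The rest of the model is flexible over time. On covariance the SAP says "An unstructured covariance matrix will be used to model the within-subject variance-covariance errors", and on inference "The comparisons of interest will be the contrasts between each active dose and placebo at every time point".

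SAP 14.3.4, 14.3.6, 14.3.8, 14.3.9 and 14.3.10 apply the same MMRM to SCORAD, pruritus NRS, DLQI, IgE and absolute eosinophil count. With EASI, that makes six continuous efficacy endpoints. EASI and NRS are percentage-change endpoints; the other four are raw change.

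**The concern.** The model lets the treatment effect, the residual variance and the correlations differ by visit, but not the relation between baseline and outcome. Neither document gives a reason for that restriction.

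For a raw-change endpoint the relation may well move. At Week 1, if little has changed, change depends only weakly on baseline. As scores approach the floor of zero, change approaches minus the baseline value and the slope moves towards -1. SAP section 6 assumes that 26% of subjects on each active dose are IGA responders at Week 12, so some approach to the floor is expected.

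If the slope does move, the fitted common slope is a compromise. At a visit whose own slope differs from it, the part of the baseline variation due to that difference stays in the residual, and so does the matching part of any chance baseline imbalance. The contrast at that visit is then less precise than the same data allow. What is at stake is the width of the 90% intervals and the power of the later-visit secondary comparisons.

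**Working it through.** **What the plan states.** Neither document gives a power, SD, baseline correlation or slope for any MMRM endpoint, so there is no MMRM figure to reproduce. The only stated power in the SAP concerns the primary endpoint: about 82% for at least one dose, with 35 per arm and rates of 26%, 26% and 6%. Exact enumeration with the pooled normal test and Hochberg at two-sided 0.10 gives 82.7%, so it reproduces. It does not depend on the MMRM.

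**Large-sample formula.** Scale baseline to SD 1. Let s be the vector of true slopes at the four visits, R the residual covariance and σ the residual SD at Week 12. The common-slope fit converges to the b that minimises log det[R + (s − b1)(s − b1)ᵀ], which is b = (1ᵀR⁻¹s)/(1ᵀR⁻¹1). The Week 12 standard error, relative to a model with visit-specific slopes, is then

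ratio = √[1 + (s₁₂ − b)²/σ²].

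All slopes and SDs below are assumptions. Drift d is the linear change in slope from Week 1 to Week 12 over the four visits.

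**Case 1: residual SD equals baseline SD (σ = 1 at every visit).** With AR(1) residual correlation, b falls at the midpoint by symmetry, so s₁₂ − b = d/2 in size, whatever the correlation.

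- d = 0.1: √(1 + 0.0025) = 1.001, or 0.12% too large
- d = 0.2: √(1 + 0.01) = 1.005, or 0.5%
- d = 0.4: √(1 + 0.04) = 1.020, or 2.0%
- d = 0.6: √(1 + 0.09) = 1.044, or 4.4%

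Squaring the last three ratios gives the equivalent in sample size: 1%, 4% and 9%.

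**Case 2: σ = 0.7 at every visit.**

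- d = 0.2: √(1 + 0.01/0.49) = 1.010, or 1.0%
- d = 0.4: √(1 + 0.04/0.49) = 1.040, or 4.0%
- d = 0.6: √(1 + 0.09/0.49) = 1.088, or 8.8%

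**Case 3: σ rises linearly from 0.5 at Week 1 to 1.0 at Week 12, correlation 0.6.** The less variable early visits pull b towards the Week 1 slope. Start the slopes at −0.2.

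- d = 0.2: b = −0.232, gap 0.168, √(1 + 0.028) = 1.014, or 1.4%
- d = 0.4: b = −0.263, gap 0.337, √(1 + 0.113) = 1.055, or 5.5%
- d = 0.6: b = −0.295, gap 0.505, √(1 + 0.255) = 1.120, or 12.0%

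Here the correlation does matter: at d = 0.6, correlations of 0.5 and 0.7 give 10.8% and 14.0%.

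**Simulation at the trial's size.** Both models were fitted by REML with unstructured covariance: 35 per arm, four visits, 9% monotone dropout (the protocol's figure), residual correlation 0.7 between adjacent visits decaying with separation, 800 trials per scenario. The table shows the empirical standard error of an active-placebo difference, visit-specific slopes divided by common slope.

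| Assumed slopes, Week 1 to 12 | Wk 1 | Wk 4 | Wk 8 | Wk 12 |
|---|---|---|---|---|
| Equal, −0.5 | 1.002 | 1.006 | 1.001 | 0.997 |
| All zero | 1.003 | 1.001 | 1.004 | 1.001 |
| Equal, skewed baseline | 1.000 | 0.999 | 1.003 | 1.002 |
| −0.40 to −0.50 | 0.996 | 1.001 | 1.002 | 0.996 |
| −0.2 to −0.6 | 0.990 | 0.990 | 0.958 | 0.926 |
| −0.1 to −0.8 | 0.988 | 0.946 | 0.858 | 0.763 |

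In the first four rows the changes run from −0.4% to +0.6%, with Monte Carlo error of 0.1 to 0.3%. With equal or zero slopes the mean model-based standard error rises by 0.1 to 0.3%, which is the price of the extra parameters. In the fifth row the Week 12 standard error falls by about 7%; a contrast with 80% power under the common slope would have about 85%. The last row, with drift of 0.7, lies beyond the range above and shows the extreme: a fall of about 24%.

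Kenward-Roger degrees of freedom were not coded, so precision was compared through empirical standard errors.

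**The case against.** The strongest reply is that nothing here is wrong. Protocol, SAP text and SAP code agree on the fixed effects, and under 1:1:1 randomisation a common baseline slope affects precision and does not bias the comparison. The endpoints are secondary and outside the Hochberg procedure, and no document gives evidence that any slope changes. All of that stands. It limits the point to an inexpensive refinement, but it gives no reason to keep the restriction.

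A reader might infer a free gain in precision for every continuous secondary endpoint. The documents do not support that. With equal slopes the gain is zero and there is a trivial loss; with drift of 0.1 and equal residual SDs the Week 12 loss from the common slope is only 0.12%. For percentage-change EASI and NRS, dividing by baseline may already remove much of the dependence, so a gain is least certain there.

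A reader might also take Week 12 EASI change to be the main continuous efficacy result. Neither document ranks the continuous endpoints. SAP 14.4.2 gives quantitative EASI at Week 12 extra sensitivity analyses, but that is not a ranking.

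Finally, the size of the effect depends on inputs chosen for the calculation. This is so: the ratio of residual to baseline SD alone doubles the range between Cases 1 and 2. The figures show what is possible and do not estimate what this trial will lose.

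**Conclusion.** The point holds as a conditional one. The plan imposes a single baseline slope at Weeks 1, 4, 8 and 12 on six continuous secondary endpoints. If the true slope drifts by 0.2 to 0.6 baseline-SD units, the Week 12 standard error is about 0.5 to 4% too large when residual SD equals baseline SD. It is about 1 to 12% too large when residual SD is smaller or grows over time (the upper figure at residual correlation 0.6). In the simulated moderate-drift case the effect at Week 1 was only about 1%. If slopes are equal there is no gain.

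These sizes rest on assumed slopes, SDs and correlations, with equal covariance across arms. A gain is plausible for SCORAD, DLQI, IgE and eosinophil count, and less certain for EASI and NRS. The analysis as planned is valid, and the primary endpoint, its power and the sample size are unaffected. This is an optional improvement and not an error.

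**What to change.** Before unblinding, add basval*visit to the MODEL statement in SAP 14.3.2 and a baseline-by-visit interaction to the list of fixed effects in the text there. The other five endpoints inherit it through their reference to the same MMRM. Because protocol 9.2.2 lists the fixed effects, add a row to SAP Table 2 recording the change and the reason. Made after unblinding, the change would look data-driven.

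Settle the response scale at the same time. The endpoint is percentage change in EASI, but the note under the code reads "ChgEASI = change from baseline in EASI for each visit". The scale determines what the baseline slope means.

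The cost is three extra parameters (four slopes instead of one), one code term, one line of text and one table row. No new data are needed. In the simulations without drift, or with only mild drift, the standard error changed by at most about 0.6%.

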3.2.2.2 Efficacy endpoints

- The percentage change in EASI score from baseline at weeks 1, 4, 8, and 12.
- The percentage of subjects who achieve IGA response at weeks 1, 4, and 8.
- The percentage of subjects whose EASI scores improve by $\geq 50\%$, 75%, and 90% (EASI50, EASI75, EASI90) from baseline at weeks 1, 4, 8, and 12.
- Changes in scoring atopic dermatitis (SCORAD) from baseline at weeks 1, 4, 8, and 12.
- The percentage of subjects whose SCORAD improve by $\geq 50\%$, 75%, and 90% (SCORAD50, SCORAD75, SCORAD90) from baseline at weeks 1, 4, 8, and 12.
- The percentage change in Pruritus Numerical Rating Scale (NRS) from baseline at weeks 1, 4, 8, and 12.
- The percentage of subjects whose NRS improve by ≥ 3 points from baseline (NRS-3) at weeks 1, 4, 8, and 12.
- Changes in Dermatology Life Quality Index (DLQI) from baseline at weeks 1, 4, 8, and 12.
- Changes in biomarker immunoglobulin E (IgE) from baseline at weeks 1, 4, 8, and 12.
- Changes in absolute eosinophil count from baseline at weeks 1, 4, 8, and 12.

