11.1 BASELINE DEFINITION AND CHANGE FROM BASELINE

Unless otherwise specified, the baseline value for a parameter of interest is the latest non-missing value prior to date of the first administration of study drug.

Change from baseline and percentage from baseline will be derived as follows:

- Change from baseline = the post-baseline value - the baseline value of a parameter of interest for a subject.
- Percentage change from baseline = (post-baseline value - the baseline value)/ baseline value of a parameter of interest for a subject.

If either the baseline or the post-baseline value is missing, then the change or percentage change will be set to missing.

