14.2 PRIMARY EFFICACY ANALYSIS

Analysis of the primary efficacy endpoint will be based on FAS.

The primary efficacy endpoint for this study is the percentage of subjects achieving IGA response at Week 12. IGA is the investigator's global assessment of the subject's general condition and consists of a 6-point severity scale from clear to very severe disease ("complete clearance", "almost

complete clearance", "mild", "moderate", "severe", and "very severe"). IGA response is defined as IGA score of 0/1 (complete or almost complete clearance of skin lesions) with an improvement in IGA score by ≥ 2 from baseline.

Subjects who early withdraw from the study for any reason will be considered as non-responders at each post-withdrawal assessment time point. Descriptive summaries of the primary efficacy endpoint will be based on non-missing data only.

Due to the impact of the COVID-2019 pandemic, subjects may have their primary efficacy endpoint assessed outside the scheduled time window of visit 6. If the primary efficacy endpoint is missing within the planned time window (between study days 82 and 88), it will be considered to impute with results of assessment within 89 to 102 study day (ie, extended visit).

The method of normal approximation to binomial will be used to test whether each active drug group is superior to the placebo group. Estimation of the difference and its 90% confidence interval between each drug group and the placebo group, as well as the corresponding p value for test will be provided.

Referenced SAS code:

```
PROC FREQ DATA = adam.adeff;  
  TABLE treat*aval/CHISQ RISKDIFF (CL = WALD) ALPHA = 0.1;  
  RUN;
```

In the above codes, variables are defined as follows:

Aval = IGA response at Week12

Treat = treatment group

In addition, IGA response and its 90% confidence interval at Week 12 will also be provided for each treatment group.

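### The reference MMRM code in SAP 14.3.2 gives 95% limits on absolute EASI change, where the text promises 90% limits on percentage change

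*SAP*

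**What the plan says.** **Endpoint.** SAP 3.2.2.2 lists "The percentage change in EASI score from baseline at weeks 1, 4, 8, and 12" as a secondary efficacy endpoint. SAP 11.1 gives the formula "Percentage change from baseline = (post-baseline value - the baseline value)/ baseline value of a parameter of interest for a subject" and, next to it, a separate definition of plain change as a simple difference.

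**Text of SAP 14.3.2.** An MMRM "will be used to analyze percentage of EASI change from baseline". For each active dose against placebo at each visit, "the model estimated least square means, standard error, p-value, and two-sided 90% confidence interval will be reported". SAP 8 sets a two-sided 0.1 level for other analyses unless stated otherwise, and nothing in 14.3.2 states otherwise.

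**Code of SAP 14.3.2.** The least-squares-means statement is "LSMEANS treat*visit/DIFF PDIFF CL". Neither it nor the PROC MIXED statement has an ALPHA= option. The response in the MODEL statement is defined as "ChgEASI = change from baseline in EASI for each visit".

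**Plot.** The same section says: "Least square means of change from baseline in EASI score at each assessment visit will be graphically displayed".

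**Comparison.** The primary-analysis code in SAP 14.2 contains "RISKDIFF (CL = WALD) ALPHA = 0.1", and the code in SAP 14.4.1 also sets ALPHA = 0.1.

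**Other endpoints.** SAP 14.3.4, 14.3.6 and 14.3.8 to 14.3.10 send SCORAD, NRS, DLQI, IgE and eosinophil count to the same MMRM as EASI. No other MMRM code is printed.

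**The concern.** The prose and the code in one section describe two different analyses, and the SAP does not say which governs. The differences concern the outcome variable of a pre-specified endpoint and the level of its confidence interval.

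If a programmer follows the code, the report would show EASI points where percent was planned, with limits at a level the SAP does not use elsewhere for efficacy. A contrast with 0.05 < p ≤ 0.10 would be significant at the SAP's 0.1 level while its printed interval includes zero. If a programmer notices and corrects the code, that correction is an undocumented choice about a secondary endpoint.

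**Working it through.** **1. Level used in the design.** SAP 6 states about 82% power with 35 per group, response rates of 26%, 26% and 6%, and Hochberg control at two-sided 0.1. Simulating 400,000 trials with a pooled z-test and counting at least one rejection gives 82.8%. The 0.1 level is therefore used consistently in the design, and the MMRM code is the exception.

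**2. Interval level.** The text needs alpha = 0.1. With no ALPHA= option, PROC MIXED uses 0.05; this is SAS behaviour, not something the documents state. The width ratio is t(0.975, df) / t(0.95, df). The Kenward-Roger degrees of freedom are not given, so 60 to 128 is assumed. For orientation, 105 − 3 − 1 = 101 from the SAP's planned number and 132 − 3 − 1 = 128 from the protocol's.

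| df | t(0.975) | t(0.95) | ratio |
|---|---|---|---|
| 60 | 2.0003 | 1.6706 | 1.197 |
| 100 | 1.9840 | 1.6602 | 1.195 |
| 128 | 1.9787 | 1.6568 | 1.194 |
| normal limit | 1.960 | 1.645 | 1.192 |

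**3. How often p-value and interval would disagree.** This happens when 0.05 < p ≤ 0.10. With 100 df the probability is 0.050 under no effect, 0.127 when the true effect is 1.8 standard errors, and 0.102 at 2.5 standard errors. These effect sizes are illustrative and do not come from the documents.

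**4. Outcome scale.** A 6-point fall in EASI is 6/12 = 50% from a baseline of 12 (the entry minimum in protocol 5.2), but 6/36 = 16.7% from a baseline of 36. The code scores both as −6. Conversely, a 50% improvement is 0.5 × 12 = 6 points at the entry minimum and 0.5 × 72 = 36 points at the scale maximum. The two scales weight patients differently, so estimates, standard errors and p-values all change with the choice.

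**5. Number of contrasts.**
- EASI in the FAS: 4 visits × 2 doses = 8.
- EASI at Week 12 in PPS and ESS (SAP 14.4.2): 2 sets × 2 doses = 4. Directly affected: 8 + 4 = 12.
- Other five endpoints, only if the code is the template: 5 × 4 × 2 = 40. Total: 12 + 40 = 52.
- Scale error beyond EASI: only NRS is also a percentage-change endpoint, so 4 × 2 = 8 more, again only if the code is the template.

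**The case against.** The strongest reply is that the plan is clear and only the sample code is wrong. Percentage change is stated in the endpoint list, the section heading, the model text and protocol 9.2.2. The 90% level is stated in the prose, and the code is offered only for reference. Harm needs a programmer to follow the block against the sentences above it. That is a fair limit on the weight of the point, but it does not remove the conflict: the SAP sets no precedence, and no code is given for the model the text specifies.

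The wider reach is also open to challenge. The same MMRM can be read as the model in the prose, which carries the 90% limits with it, and the NRS section is headed as a percent change. The counts beyond the 12 EASI contrasts are therefore conditional.

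The plot could be a deliberate display of absolute change beside a percentage analysis. But least-squares means come from a fitted model, and the text defines that model only for percentage change. Either the plot's scale is a slip or a second model is missing. Finally, no decision rule uses these intervals, which is correct.

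**Conclusion.** Both mismatches hold. Run as printed, the code gives 95% limits, about 19% to 20% wider than the promised 90% limits, and analyses absolute instead of percentage EASI change. The width figure rests on the SAS default of 0.05 and on assumed degrees of freedom of 60 to 128, and it hardly moves across that range. Twelve EASI contrasts are affected directly; 52 would be if the block is the template for all MMRM endpoints.

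The ALPHA omission does not alter point estimates, standard errors or p-values; the scale mismatch alters all three. The primary IGA analysis, the Hochberg procedure and the design are unaffected. The risk is misreported secondary results, not a changed trial conclusion. SAP Table 2 declares no move to absolute change, so nothing suggests that one was intended.

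**What to change.** - Add ALPHA=0.1 to the LSMEANS statement in SAP 14.3.2.
- Define the dependent variable as percentage change, per SAP 11.1, for EASI and NRS, and as absolute change for SCORAD, DLQI, IgE and eosinophil count.
- State the scale of the EASI least-squares-means plot. If absolute change is wanted there, say that a separate MMRM of absolute change supplies it.
- Two copy-edits: label the confidence interval in SAP Table 6 (a decimal-places table) as 90%, and let the autoregressive fallback name one structure, since AR(1) and heterogeneous autoregressive are different. Use ARH(1) if heterogeneous is meant.

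The cost is a few lines of SAP wording and code. Design, data collection and the primary analysis do not change.
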